3.5. Data Handling Conventions and Transformations

- By-subject listings will be created for important variables in each eCRF module, and sorted by subject number, visit, and time (if applicable).
- Summary tables for continuous variables will contain the following statistics: N (number in analysis set), n (number with data), mean, standard deviation (StD), median, Q1, Q3, minimum, and maximum. The same number of decimal places as in the raw data will be presented when reporting minimum and maximum, 1 more decimal place than in the raw data will be presented when reporting mean, median and 2 more decimal places than in the raw data will be presented when reporting StD.
- Summary tables for categorical variables for baseline and safety data will include: N, n, percentage. The tables for efficacy endpoints will include standard error, and 95% confidence intervals (CI) on the percentage, where appropriate. Unless otherwise indicated, 95% CIs for binary variables will be calculated using the binomial distribution. The denominator for the percentages will be the number of subjects in the specified analysis set at the same treatment or total as appropriate, unless otherwise specified. Missing data will be included as a row in tables where it is appropriate. All percentages will be presented as 1-decimal point, unless otherwise specified. Percent equal to 100 will be presented as 100% and percent will not be presented for zero frequencies.
- Data from all sites will be pooled for all analyses.

- Analyses will be based upon the observed data unless methods for handling missing data are specified.
- For Kaplan-Meier estimates, the 95% CIs will be calculated using the Greenwood's formula with (complementary) log-log transformation.

3.5.1. Data Handling for Treatment Groups

Subjects who developed disease progression, confirmed by independent review committee (IRC), in Study GS-US-312-0116 could consider participation in Study GS-US-312-0117. Upon enrollment, subjects who were randomized into Arm A received IDELA 300 mg BID and those who were randomized into Arm B received IDELA 150 mg BID.

Study GS-US-312-0116 was stopped early due to overwhelming efficacy based on results from the first interim analysis and the primary study was unblinded. Under the protocol amendment, all remaining subjects were given the opportunity to enroll in Study GS-US-312-0117 and received IDELA 150 mg BID. The dose increase to IDELA 300 mg BID after confirmed PD on Arm A was no longer offered.

For disposition data summaries, subjects will be assigned into 1 of the following 4 treatment groups:

- IDELA 150 mg BID in GS-US-312-0116 and GS-US-312-0117:
 - Includes all subjects who are randomized to Arm A in Study GS-US-312-0116 except for those who take IDELA 300 mg BID in Study GS-US-312-0117
 - Referred to 'IDELA+R/IDELA' throughout this SAP and the tables, figures, and listings (TFLs)
 - Baseline for efficacy endpoints will be the date of randomization in Study GS-US-312-0116.
 - Baseline for safety endpoints will be the first dosing of IDELA in Study GS-US-312-0116.
 - In the analysis, the Study GS-US-312-0117 portion will include all the data collected on or after the enrollment date of Study GS-US-312-0117.
- IDELA 150 mg BID in GS-US-312-0116 + IDELA 300 mg BID in GS-US-312-0117:
 - Includes subjects who experience IRC confirmed progressive disease (PD) in Arm A of Study GS-US-312-0116 and subsequently enroll into Study GS-US-312-0117 to receive IDELA 300 mg BID during the double-blind portion of the study
 - Referred to 'IDELA+R (PD)/IDELA' throughout this SAP and the TFLs

- Baseline for efficacy and safety endpoints will be the first dosing of IDELA 300 mg BID, unless otherwise specified.
- In the analysis, the Study GS-US-312-0117 portion will include all the data collected on or after the enrollment date of Study GS-US-312-0117.
- Placebo in GS-US-312-0116 + IDELA 150 mg BID (open-label):
 - Includes subjects who are randomized to Arm B in Study GS-US-312-0116 and transition to receive IDELA 150 mg BID during the open-label portion of the study
 - Referred to 'Placebo+R/IDELA' throughout this SAP and the TFLs
 - Baseline for efficacy and safety endpoints will be the first dosing of IDELA, unless otherwise specified.
 - In the analysis, the Study GS-US-312-0117 portion will include all the data collected on or after the first dosing date of IDELA. The Study GS-US-312-0117 portion may include data collected in Study GS-US-312-0116, if a subject switches to open-label IDELA in Study GS-US-312-0116 while waiting for the protocol amendment.
- Placebo in GS-US-312-0116 + IDELA 150 mg BID in GS-US-312-0117:
 - Includes subjects who experience IRC confirmed PD in Arm B of Study GS-US-312-0116 and subsequently enroll into Study GS-US-312-0117 to receive IDELA 150 mg BID during the double-blind portion of the study
 - Referred to 'Placebo+R (PD)/IDELA' throughout this SAP and the TFLs
 - Baseline for efficacy and safety endpoints will be the first dosing of IDELA, unless otherwise specified.
 - In the analysis, the Study GS-US-312-0117 portion will include all the data collected on or after the enrollment date of Study GS-US-312-0117.

Efficacy and safety data collected during the primary and extension studies will be presented in the following 3 treatment groups:

- IDELA+R (PD, non-PD)/IDELA
 - Includes all subjects who are randomized to Arm A in Study GS-US-312-0116 (ie, all subjects in IDELA+R/IDELA and IDELA+R (PD)/IDELA)
 - For those in IDELA+R (PD)/IDELA, only data collected in Study GS-US-312-0116 (ie, while taking IDELA 150 mg BID) will be included. For those in IDELA+R/IDELA, all the data collected across Study GS-US-312-0116 and GS-US-312-0117 will be included. By this summary, the efficacy and safety profile of IDELA 150 mg BID can be explored for subjects randomized to Arm A in Study GS-US-312-0116.

- Baseline for efficacy endpoints will be the date of randomization in Study GS-US-312-0116.
- Baseline for safety endpoints will be the first dosing of IDELA 150 mg BID in Study GS-US-312-0116.
- Placebo+R/IDELA
- Placebo+R (PD)/IDELA

Due to the small sample size (N = 4) for the IDELA + R (PD)/IDELA group, data collected from this group in Study GS-US-312-0117 (ie, while taking IDELA 300 mg BID) will only be presented in listings.

Baseline for each data summary is described in Table 3-1.

	Baseline for Disposition Summary		Baseline for Efficacy Summary		Baseline for Safety Summary
Treatment Group	312-0116	312-0117	All endpoints except for OS	OS	All endpoints
IDELA+R/IDELA	Date of randomization in Study GS-US-312-0116	Enrollment date of Study GS-US-312-0117	Date of randomization in Study GS-US-312-0116		First dosing date of IDELA in Study GS-US-312-0116
IDELA+R (PD)/IDELA	Date of randomization in Study GS-US-312-0116	Enrollment date of Study GS-US-312-0117	First dosing date of IDELA 300 mg BID in Study GS-US-312-0117		First dosing date of IDELA 300 mg BID in Study GS-US-312-0117
Placebo+R/IDELA	Not applicable	First dosing date of IDELA (Switching date to open-label IDELA)	First dosing date of IDELA (Switching date to open-label IDELA)	Date of randomization in Study GS-US-312-0116	First dosing date of IDELA (Switching date to open-label IDELA)
Placebo+R (PD)/IDELA	Not applicable	Enrollment date of Study GS-US-312-0117	First dosing date of IDELA 150 mg BID in Study GS-US-312-0117		First dosing date of IDELA 150 mg BID in Study GS-US-312-0117
IDELA+R(PD, non-PD)/ IDELA	Not applicable	Not applicable	Date of randomization in Study GS-US-312-0116		First dosing date of IDELA in Study GS-US-312-0116

Table 3-1.Baseline for Data Summaries by Treatment Group

Data from subjects who are randomized to Arm B in Study GS-US-312-0116 and never received IDELA in Study GS-US-312-0117 will be excluded from the analyses, unless otherwise specified.

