Note: At the Investigator's discretion, subjects who were randomized to placebo on study GS-US-312-0116 may delay initiation of idelalisib following enrollment on Study GS-US-312-0117 until the time of disease progression or until the investigator determines that the subject would benefit from initiation of idelalisib treatment

Reference Therapy, Dose, and Mode of Administration:

Not applicable

Criteria for Evaluation:

Tumor Control

- Progression-free survival (PFS) defined as the interval from the start of study therapy to the earlier of the first documentation of definitive disease progression or death from any cause; definitive disease progression is CLL progression based on standard criteria other than lymphocytosis alone
- Overall response rate (ORR) defined as the proportion of subjects who achieve a complete response (CR) or partial response (PR)
- Lymph node response rate defined as the proportion of subjects who achieve a ≥50% decrease from baseline in the sum of the products of the greatest perpendicular diameters (SPD) of index lesions
- CR rate defined as the proportion of subjects who achieve a CR
- Time to response (TTR) defined as the interval from start of study therapy to the first documentation of CR or PR
- Duration of response (DOR) defined as the interval from the first documentation of CR or PR to the earlier of the first documentation of definitive disease progression or death from any cause
- Percent change in lymph node area defined as the percent change from baseline in the SPD of index lymph nodes
- Splenomegaly response rate defined as the proportion of subjects with baseline splenomegaly who achieve an on-study normalization or a 50% decrease (minimum 2 cm) from baseline in the enlargement of the splenic LVD (by imaging)

- Hepatomegaly response rate defined as the proportion of subjects with baseline hepatomegaly who achieve an on-study normalization or a 50% decrease (minimum 2 cm) from baseline the hepatic longest vertical dimension (LVD) (by imaging)
- ALC response rate defined as the proportion of subjects with baseline lymphocytosis (ALC≥4 x 10⁹/L) who achieve an on-study ALC <4 x 10⁹/L or demonstrate a ≥50% decrease in ALC from baseline (ALC values within 4 weeks post-baseline will be excluded from the ALC response rate evaluation)

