Compliant subjects who are tolerating therapy but who develop definitive disease progression in the primary clinical trial (Study GS-US-312-0116) can consider enrollment in this separate companion extension trial (Study GS-US-312-0117). In the extension trial, subjects will take active blinded idelalisib therapy, either at a higher starting dose or at the standard starting dose, with allocation based on the original primary study randomization. Following unblinding of Study GS-US-312-0116, subjects will be allowed to enter Study GS-US-312-0117 in the absence of evidence of disease progression and will take 150 mg BID idelalisib regardless of treatment assignment in Study GS-US-312-0116.

The primary objective of Study GS-US-312-0116 will be to evaluate the effect of the addition of idelalisib to rituximab on PFS. Secondary and tertiary objectives will focus on determining the effect of the addition of idelalisib to rituximab on the onset, magnitude, and duration of tumor control; overall survival (OS); health-related quality of life (HRQL); changes in subject performance status; disease-associated biomarkers and potential mechanisms of resistance; treatment administration; safety; and health resource utilization. In Study GS-US-312-0117, the same endpoints will be assessed as in Study GS-US-312-0116; the focus of the analysis will be largely descriptive except for the within-subject assessment of treatment effects among subjects receiving first rituximab alone and then idelalisib alone on Arm B of each trial. No formal comparisons of outcomes in Arm A vs Arm B are planned within Study GS-US-312-0117.

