4.3. Enrollment Criteria Rationale

The eligibility criteria are designed to limit enrollment to subjects who participated in the primary clinical trial (Study GS-US-312-0116), are compliant, have been generally able to tolerate study therapy and study procedures, and have experienced definitive CLL progression while receiving study treatment (rituximab and/or idelalisib/placebo) in the primary study or who are actively participating in Study GS-US-312-0116 at the time the study is stopped, including if stopped early due to overwhelming efficacy.

The requirement of measurable lymphadenopathy to enter the blinded portion of the study ensures that subjects have disease that can adequately be assessed for evidence of drug activity. Prior therapy provisions are intended to ensure that subjects are transitioning directly from Study GS-US-312-0116 to Study GS-US-312-0117 without receiving intervening treatments. The stipulation of ≤12-week interval from Study GS-US-312-0116 treatment until Study GS-US-312-0117 treatment precludes excessively protracted intervals between participation in the 2 studies but also permits sufficient time for clinicians and subjects to determine whether participation is appropriate.

In the blinded portion of the study, to ensure that subjects are not so acutely ill from life-threatening comorbidities that they require hospitalization and stabilization, subjects with Karnofsky performance scores <40 (ie, those who are bed-bound or hospitalized) will not be enrolled. Baseline laboratory evaluations are designed to limit participation to subjects who have not developed serious organ compromise that would pose a safety risk or confound the interpretation of adverse effects. Pregnancy testing and restrictions on eligibility relating to reproduction, pregnancy, and nursing are important because idelalisib is a new chemical entity with teratogenic effects in rats and it is unknown if it may have adverse effects on conception, on fetal development, or on the health of a breast-feeding child. To minimize missing data and premature discontinuations, subjects should have sufficient psychological and social resources to comply with study procedures and restrictions. Consistent with GCP guidelines, subjects must provide informed consent before initiation of any study procedures.

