7.5. Definitions of Tumor Response and Progression

Responses will be categorized by the IRC as CR, PR, SD, or PD. In addition, a response category of not evaluable (NE) is provided for situations in which there is inadequate information to otherwise categorize response status. A response category of no disease (ND) is included for situations in which there is absence of tumor both at baseline and on treatment.

The best overall response will be determined. The best overall response is the best response recorded from the start of treatment until disease/recurrence progression (taking as a reference for disease progression the smallest measurements recorded since treatment started). Subjects with a best overall response of NE or ND will be counted in the denominators in calculations of tumor response rates.

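### Placebo+R/IDELA pools open-label starters with and without progression on a reset baseline, so its ORR, PFS and DOR are a mixture and cannot be read as the effect of idelalisib alone

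*SAP*

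**What the plan says.** SAP 3.5.1 says that Placebo+R/IDELA "Includes subjects who are randomized to Arm B in Study GS-US-312-0116 and transition to receive IDELA 150 mg BID during the open-label portion". For this group, "Baseline for efficacy and safety endpoints will be the first dosing of IDELA, unless otherwise specified"; Table 3-1 confirms that only OS keeps the randomization date. SAP 6.1.1 runs PFS and TTR from that reference date, and SAP 6.1.2.6 takes the last SPD before it as baseline. Counted data "may include data collected in Study GS-US-312-0116, if a subject switches to open-label IDELA in Study GS-US-312-0116 while waiting for the protocol amendment".

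Protocol 2.1 states that after unblinding "subjects will be allowed to enter Study GS-US-312-0117 in the absence of evidence of disease progression". Former placebo subjects need not start at once: at the investigator's discretion they "may delay initiation of idelalisib following enrollment on Study GS-US-312-0117 until the time of disease progression", or until the investigator judges that they would benefit (Protocol synopsis, test therapy note; Protocol 5.1.2).

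The companion group, Placebo+R (PD)/IDELA, is confined to IRC-confirmed progressors who enrolled during the double-blind portion. SAP 3.3 plans efficacy subgroups by 17p deletion and p53 mutation only.

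**The concern.** The first listed objective is the onset, magnitude and duration of tumor control with idelalisib, and Placebo+R/IDELA is one of only three groups in which the SAP presents efficacy. The labels suggest a progressed group and a non-progressed group, but the second contains both kinds of subject.

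The two kinds start from different places. A subject still benefiting from rituximab may have little disease left to shrink, or may have a rituximab response that is still deepening and is then counted after the reset. A subject who waited for progression starts with growing disease. Protocol 4.3 recognizes why this matters: "The requirement of measurable lymphadenopathy to enter the blinded portion of the study ensures that subjects have disease that can adequately be assessed". That safeguard was not carried into the open-label route. A single rate or curve for the group therefore does not say what idelalisib did in either kind of subject.

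**Working it through.** The plan gives no power, effect size or target for this group, so there is no figure to reproduce. The check is of the text, with two supporting calculations.

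**1. Entry conditions side by side (Protocol synopsis, 4.2.1)**

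| Condition | Blinded route | Open-label route |
|---|---|---|
| Confirmed progression | Required | Not required |
| Measurable node, at least 2.0 × 1.0 cm | Required | Not required |
| Permanent cessation of 0116 treatment | Required | Not listed |
| Timing | At most 12 weeks from stopping 0116 treatment | In 0116 within 12 weeks of enrollment |

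Rituximab in the primary study runs to Week 20, eight infusions in all (Protocol 2.1). The open-label route sets no minimum interval from the last infusion to the first idelalisib dose.

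**2. Where a delayed starter goes.** A former placebo subject who enrolls after unblinding, waits and progresses cannot enter Placebo+R (PD)/IDELA, which is tied to the double-blind portion. That subject stays in Placebo+R/IDELA.

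**3. Floor on nodal shrinkage.** Protocol 7.4.1 assigns 1.0 cm to any node diameter above 0 and below 1.0 cm, so a small visible node counts as 1.0 cm². Unless nodes disappear:

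maximum fall = 1 − (number of nodes × 1.0) / baseline SPD

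- One node at the blinded-entry minimum, 2.0 × 1.0 cm: 1 − 1/2.0 = 50.0%, exactly the threshold.
- One node just above the index-lesion minimum, 1.51 × 1.0 cm: 1 − 1/1.51 = 33.8%, below the threshold.
- Six visible nodes: floor 6 cm², so a baseline SPD below 12 cm² cannot show a 50% fall.

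A subject already reduced by rituximab can thus be unable to meet the nodal criterion yet remain in the ORR denominator. SAP 6.1.2.2 also keeps subjects with insufficient assessments there, and Protocol 7.5 states: "Subjects with a best overall response of NE or ND will be counted in the denominators".

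**4. Illustrative ORR mixture.** Let f be the share starting without progression and q their ORR from the new baseline. Both are assumptions. For progressors, use the single-agent Phase 1 CLL rate in Protocol 1.3.5.2.1, 39/54 = 72.2%.

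pooled ORR = (1 − f) × 0.722 + f × q

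| f | q = 10% | q = 50% | q = 95% |
|---|---|---|---|
| 25% | 56.7% | 66.7% | 77.9% |
| 50% | 41.1% | 61.1% | 83.6% |
| 75% | 25.6% | 55.6% | 89.3% |

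**5. Illustrative PFS mixture.** Assume exponential PFS with a median of 12 months in progressors, median m in non-progressors, and f = 50%. Solving 0.5 × 2^(−t/12) + 0.5 × 2^(−t/m) = 0.5 gives a pooled median of 9.7, 14.6 or 16.7 months for m = 8, 18 or 24. None of these medians comes from the documents; they show only that the pooled median can move either way.

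**The case against.** The strongest reply is that the plan claims little for this group. SAP 3.5.2 makes all analyses descriptive with no formal group comparison. The group is kept apart from Placebo+R (PD)/IDELA, and the between-study PFS and ORR tables (SAP Appendix 1, Tables 2.1.7 and 2.2.6) use only the latter. Grouping by entry route is defensible, since delayed starters did not have to meet the blinded route's requirements and so are not interchangeable with that group. All of this stands and limits the weight of the point. It does not supply the missing split.

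Some stronger readings are tempting but unsupported:

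- A reader might infer that a subject already in complete remission at the new baseline is credited to idelalisib at the first scan. Protocol 7.5.6 and SAP 6.1.2.2 provide a no-disease category for subjects without evidence of disease at baseline and on treatment, separate from CR and PR. Such subjects lower the ORR; they do not raise it.
- A reader might take the ORR of non-progressors to be near zero. Protocol 7.5.2 generally asks for two of five criteria (lymphocytes, nodes, spleen, liver, marrow), so PR can be reached without nodal response. It hinges on nodes only when nodes, or nodes plus lymphocytosis, are the sole baseline findings. Zero is a worst case.
- A reader might suppose that subjects receive rituximab throughout the counted period. Protocol 5.6.1 bars antibody therapy in the extension. Overlap is conceivable only in counted primary-study time, "if a subject switches to open-label IDELA in Study GS-US-312-0116 while waiting for the protocol amendment", and then only before the rituximab course ended. The documents do not show that any such subject exists. Residual effect is the firmer ground.
- A reader might want every denominator changed. LNR already needs a baseline and a post-baseline SPD (SAP 6.1.2.3), and TTR is computed in responders only (SAP 6.1.2.5).

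**Conclusion.** The point holds in this form: Placebo+R/IDELA combines subjects in different disease states on a baseline reset to the first idelalisib dose, with no planned separation, so its pooled ORR, PFS and DOR cannot be read as the effect of idelalisib alone. Subjects who start at progression, well after rituximab, do contribute single-agent information, which is a reason to show them separately.

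The size and direction are indeterminate. The illustrated ORR range of 25.6% to 89.3% rests on assumed shares and assumed non-progressor rates, and the PFS figures on assumed medians; none is an estimate of actual bias. The point is moderate: no hypothesis test is affected, but it changes what this group can contribute to the first objective.

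**What to change.** In SAP 3.3, 3.5.1 and 6.1.2, for Placebo+R/IDELA:

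1. Present PFS, ORR, LNR, TTR and DOR separately for subjects with and without documented definitive progression before the first idelalisib dose. State which reading decides; the IRC finding fits SAP Section 6. Leave the LNR and TTR denominators as they are.
2. Tabulate time from last rituximab infusion to first idelalisib dose, and flag any subject given rituximab on or after that dose in counted primary-study time.
3. Add a supplementary ORR and CR rate in subjects with at least one index node at the new baseline, and keep the all-subject rates.
4. Label the pooled result as a mixture of disease states.

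This is SAP wording and extra table columns. It should need no new data collection, since IRC status, node measurements and dosing dates should already be held. The cost is smaller subgroups with wider intervals.

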3.1.2. Full Analysis Set

The full analysis set (FAS) includes all subjects in the ITT analysis set who receive ≥ 1 dose of IDELA, with treatment assignments designated according to randomization. Because all the subjects received correct treatment as randomized, this analysis set will be used for both the efficacy and safety analyses.

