7.6. Changes From Protocol-Specified Safety Analyses

Summary of study drug compliance will be removed as the accurate calculation of drug accountability is not feasible for subjects who cross over to open-label IDELA in Study GS-US-312-0116.

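### SAP 3.5.1 excludes Arm B subjects by whether they took idelalisib in Study 0117, but their clock and the FAS start at first dose in either study, so early failures among Study 0116 switchers could be dropped

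*SAP*

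**What the plan says.** SAP 3.1.2 defines the FAS as "all subjects in the ITT analysis set who receive ≥ 1 dose of IDELA" and uses it for safety and for efficacy. It does not say which study must have supplied the dose.

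For Placebo+R/IDELA, SAP 3.5.1 puts baseline at the first idelalisib dose and states that "the Study GS-US-312-0117 portion will include all the data collected on or after the first dosing date of IDELA". That portion may reach back into the primary study "if a subject switches to open-label IDELA in Study GS-US-312-0116 while waiting for the protocol amendment". Table 3-1 gives the date of the switch as time zero for this group, for safety and for every efficacy endpoint except OS. SAP 7.6 drops the compliance summary because accountability cannot be calculated for "subjects who cross over to open-label IDELA in Study GS-US-312-0116", so the authors treat such switching as real.

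The sentence after Table 3-1 then says that subjects "randomized to Arm B in Study GS-US-312-0116 and never received IDELA in Study GS-US-312-0117 will be excluded from the analyses", with an exception for anything specified otherwise. OS is specified otherwise: SAP 3.1.1 and 6.1.2.8 analyse all randomized subjects by original arm.

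**The concern.** A population rule should not depend on something that happens after time zero. Here time zero can be a dose taken in Study 0116, while staying in the analysis appears to require a later dose in Study 0117. A subject who failed in between would be lost, and one who did not fail would be kept.

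Placebo+R/IDELA is one of only three groups in which efficacy and safety are reported. It is tabulated beside an Arm A group that includes everyone randomized to that arm, whether or not they entered 0117. In the FAS tables, early failures on idelalisib would therefore count in Arm A and might not count among Arm B switchers. Deaths and treatment stops on open-label idelalisib are what the safety tables exist to show.

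**Working it through.** No sample size, power or alpha in the plan depends on this rule, so there is no figure to reproduce. The check is to take each kind of subject through the two rules.

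| Subject | FAS (3.1.2) | Exclusion sentence, read literally (3.5.1) | Agree? |
|---|---|---|---|
| Arm B, no idelalisib in either study | out | out | yes |
| Arm B, first idelalisib dose in 0117 | in | kept | yes |
| Arm B, switched in 0116, later dosed in 0117 | in | kept, clock from the 0116 switch | yes |
| Arm B, switched in 0116, died or stopped permanently before any 0117 dose | in | out | **no** |
| Arm A | in if dosed | does not apply | yes |

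Only the fourth row conflicts. Its counterpart is the third row, where subjects are kept because they reached 0117 dosing. For them, the gap between switch and 0117 dosing cannot contain a death or a permanent stop. Placebo+R (PD)/IDELA has no such gap, because its time zero is "First dosing date of IDELA 150 mg BID in Study GS-US-312-0117".

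**What fourth-row subjects would take with them.** They would take deaths and progressions that ended treatment (PFS), non-responders who count in the ORR denominator under SAP 6.1.2.2, short exposures, discontinuations, and fatal or treatment-ending adverse events. Losing deaths, treatment-ending progressions and discontinuations makes the summaries look better. For a subject who stopped for toxicity without progressing, the effect on PFS depends on later follow-up.

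**Scale, for illustration only.** The documents give neither the number of 0116 switchers nor the length of the gap. Assume:

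- exponential event times, S(t) = exp(−λt), with λ = ln 2 / (median in months × 4.345 weeks per month);
- a share f of the group switched in 0116;
- 0117 dosing starts at week g after the switch;
- any event in the gap removes the subject.

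Then:

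share dropped = f × [1 − S(g)]

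reported S(t) = S(t) / {1 − f × [1 − S(g)]}

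Worked case, median 12 months, g = 8, f = 0.5: λ = 0.6931/52.14 = 0.01329 per week, S(8) = 0.899, share dropped = 0.5 × 0.101 = 5.0%, S(24) = 0.727, reported S(24) = 0.727/0.950 = 0.765.

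| Assumed median, g, f | Share dropped | 24 weeks: true, reported | 48 weeks: true, reported |
|---|---|---|---|
| 18 months, 4 weeks, 0.25 | 0.9% | 80.8%, 81.5% | 65.4%, 65.9% |
| 12 months, 8 weeks, 0.5 | 5.0% | 72.7%, 76.5% | 52.8%, 55.6% |
| 6 months, 12 weeks, 1.0 | 27.3% | 52.8%, 72.7% | 27.9%, 38.4% |

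The 24-week inflation runs from 0.7 to 19.9 points. If some gap events do not end dosing, those subjects are kept and the inflation is smaller.

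**The case against.** The best defence is that the provisions specific to this group point the other way. SAP 3.5.1 defines the group's 0117 portion as everything from first idelalisib dose, including data collected in 0116. Table 3-1 uses the switch, not enrolment, as its 0117 disposition baseline. On that view, receiving idelalisib in 0117 means receiving it in the 0117 portion, and no switcher is excluded. This is a coherent reading, so the defect is an unresolved contradiction and not a settled exclusion. It does not remove the problem: the same section uses the study number for the place of dosing when it describes the switch within 0116, and two programmers could build different populations from this text.

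Three stronger inferences are tempting, and the documents do not support them.

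- *That the SAP drops all these Arm B subjects from every analysis.* The sentence carries an exception, and OS with its crossover sensitivity analyses uses the ITT set. Arm B subjects with no idelalisib in either study are properly left out of summaries that start at first idelalisib dose.
- *That the gap is free of all events, so early hepatotoxicity is hidden.* Only death or permanent discontinuation prevents later dosing. Treatment-emergent events count from the start of idelalisib (SAP 7.1.5.1), so non-fatal events that did not stop dosing remain. Protocol 1.3.5.2.1 describes the transaminase elevations as reversible, with 9 of 14 rechallenged subjects resuming without recurrence. Protocol 6.2.2 lets drug holds from 0116 continue at Visit 2.
- *That early failures were in fact excluded.* Nothing shows that any subject took idelalisib only in 0116.

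Planned Table 1.4 (analysis sets) and Listing 1.3 (subjects excluded from any analysis set) might reveal an exclusion afterwards. They do not say which rule applies.

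**Conclusion.** The point stands as a contradiction between SAP 3.5.1 and SAP 3.1.2 over who is analysed in the Placebo+R/IDELA group. Under the literal wording, the descriptive PFS, discontinuation and death summaries for that group would favour idelalisib, and response and exposure would be computed on a selected set. The effect is confined to Arm B subjects who switched within Study 0116.

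The size is unknown and may be zero. The 0.7 to 19.9 point range rests entirely on assumed medians, gap lengths and switching shares. It shows that the rule can matter; it does not estimate what happened in this trial. No formal comparison is at risk, since SAP 3.5.2 plans none. Because the sentence decides who enters the efficacy and safety tables, it should be settled before those tables are programmed.

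**What to change.** Replace the exclusion sentence with wording that matches the FAS, for example: *Arm B subjects with no idelalisib dose in either Study GS-US-312-0116 or Study GS-US-312-0117 are left out of the FAS-based analyses.* State that any Arm B subject who started open-label idelalisib in 0116 belongs to Placebo+R/IDELA from that dose, including anyone who never enrolled in 0117. Add one line to the disposition table giving the number dosed only in 0116.

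The cost is one sentence, one derivation flag and one count, since SAP 3.5.1 already provides for 0116 data in this group. If the count is zero, reporting it closes the question.
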